3.3.10. Time to Death

For analysis of time to death, the time to death will be defined as the elapsed time (in days) from randomization to death. For the safety analysis, this will be elapsed time (in days) from the first dose of study treatment (interferon beta-1a, remdesivir, or placebo).

Any subjects that are lost to follow-up or terminated early prior to death will be censored at the day of their last observed assessment or last captured event (e.g. the end date of an adverse event). Subjects who complete follow-up will be censored at the earliest of their Day 29 visit and (actual) Day 29. Deaths that occur after Day 29 will be censored at Day 29.

Similar censoring methods will be used for the 14-day mortality analyses in that deaths that occur after Day 15 will be censored at Day 15 and subjects who are confirmed alive through Day 15 will be censored at Day 15. Subjects whose last observed assessment or last capture event (e.g. the end date of an adverse event) is prior to Day 15 will be censored at that last observed assessment/event.

3.3.11. Composite Endpoint of Death, SAEs, Severe AEs

A safety composite endpoint will be defined as the occurrence of at least one of the following through Day 29:

1. Death
2. SAE
3. Grade 3 or 4 AE

The time to this composite endpoint will be defined as the elapsed time (in days) from the day of the first dose of study treatment (interferon, remdesivir, or placebo) to the earliest date of any of the events. Any subjects that are lost to follow-up or terminated early prior to experiencing any of the events will be censored at the day of their last observed assessment. Subjects who complete follow-up but do not experience any of the events will be censored at the Day 29 visit.

4. INVESTIGATIONAL PLAN

4.1. Overall Study Design and Plan

ACTT-3 will evaluate the combination of interferon beta-1a and remdesivir compared to remdesivir alone. Subjects will be assessed daily while hospitalized. If the subjects are discharged from the hospital, they will have a study visit at Days 15, 22, and 29. For discharged subjects, it is preferred that the Day 15 and 29 visits are in person to obtain safety laboratory tests and OP swab and blood samples for secondary research as well as clinical outcome data. However, infection control or other restrictions may limit the ability of the subject to return to the clinic. In this case, post-discharge visits may be conducted by phone call, home visit or remote telehealth procedure as per institutional standards. If the Day 15 and 29 visits are conducted by phone or remotely, only clinical data will be obtained (i.e., no specimens collected). The Day 22 visit does not have laboratory tests or collection of samples and is conducted by phone or remote telehealth procedure unless the subject is still hospitalized at Day 22 and then the visit is conducted in person.

4.2. Selection of Study Population

Male and non-pregnant female adults ≥ 18 years of age or older with COVID-19 and who meet all eligibility criteria will be enrolled at up to approximately 100 clinical trial sites globally. The target population should reflect the community at large.

See Section 5.1 and 5.2 of Appendix C of the study protocol for the full list of inclusion and exclusion criteria.

4.2.1. Treatments Administered

All subjects will receive remdesivir as a 200 mg intravenous (IV) loading dose on Day 1, followed by a 100 mg once-daily IV maintenance dose for the duration of the hospitalization. Enrollment may proceed for subjects who received one or two doses of remdesivir under EUA or similar mechanism prior to randomization. If subjects already received the loading dose, then the Day 1 dose will be 100 mg. Any doses of remdesivir under an EUA (or similar mechanism) within 1 week of enrollment will be counted, so the maximum number of remdesivir doses given to a subject is 10 (i.e., EUA doses + doses on this trial). See protocol Appendix C Section 6.1.2.

For the subcutaneous interferon beta-1a / placebo component, subjects will receive either active product or placebo as follows:

- Interferon beta-1a will be administered every other day as a 44-microgram subcutaneous dose for a total of 4 doses while hospitalized
- A saline placebo will be administered every other day as a subcutaneous injection for a total of 4 doses while hospitalized

4.2.2. Identity of Investigational Product(s)

See Section 6.1.1 of Appendix C of the study protocol.

4.2.3. Method of Assigning Subjects to Treatment Groups (Randomization)

Randomization will be stratified by:

- Site
- Severity of illness at randomization (by ordinal scale)
 - Hospitalized, on non-invasive ventilation or high flow oxygen devices.
 - Hospitalized, requiring supplemental oxygen, or
 - Hospitalized, not requiring supplemental oxygen.

Note: Category 7 (hospitalized, on invasive mechanical ventilation/ECMO) and Category 6 (hospitalized, on non-invasive ventilation or high flow oxygen devices) are not eligible for enrollment in protocol version 8.0. See description of recommendations made by the DSMB on September 4, 2020 below.

There was the hypothetical concern that interferon may worsen the pro-inflammatory state seen in COVID-19 late in the clinical course of the disease. For this reason, enrollment was staged based on severity of disease.

- For the first 2 weeks of the study, enrollment was limited to non-intubated, hospitalized COVID-19 patients who meet all eligibility criteria (i.e., patients with baseline ordinal scale score of 4, 5 or 6).
- On September 4, 2020, the DSMB met for an interim safety review of the ACTT-3 data. After their review, they notified NIAID that their recommendation was to close further enrollment to patients with a baseline ordinal score of 6. The DSMB noted there was no increase in mortality in this group, but that the risk/benefit in this group did not warrant further enrollment. Specifically, it was recommended by the DSMB:
 - No further enrollment of subjects with ordinal score of 6 at time of randomization.
 - Do not enroll subjects with ordinal score of 7 at time of randomization
 - Continue to enroll patients with a baseline ordinal score of 4 and 5.
- Furthermore, the DSMB recommended:
 - Subjects currently enrolled who have an ordinal score of 6, should not be given any more study injections (interferon/placebo) for the remainder of the study.
 - Subjects enrolled as a baseline ordinal 4 or 5 and remain as ordinal 4 or 5, should continue to receive study injections (interferon/placebo) and remdesivir per protocol.
 - If a subject enrolled as a baseline ordinal 4 or 5 and progresses to ordinal 6 or 7, the study injections (interferon/placebo) should be discontinued for the remainder of the study. In this case, the remdesivir infusions would continue per protocol. Importantly, all subjects should remain in the study and followed through day 29 in accordance with the protocol.

4.2.4. Selection of Doses in the Study

The dose of remdesivir used in this study will be the same dose that has been used in the human Ebola clinical trials and as in ACTT-1 and ACTT-2 studies.

The subcutaneous 44 mcg dose of Rebif is the dose that has been used in other COVID-19 clinical trials including the World Health Organization's Solidarity Trial.

4.2.5. Selection and Timing of Dose for Each Subject

See Sections 6.1.2 through 6.1.5 of Appendix C of the study protocol.

4.2.6. Blinding

As both arms are receiving remdesivir, the remdesivir product is not blinded and study infusions are labeled accordingly.

The subcutaneous interferon beta-1a/matching placebo component is blinded. Interferon beta-1a and placebo will be identical in appearance.

Unblinding of the study will occur after all subjects randomized have reached the end of study, and these visits are monitored and data is cleaned, or if the DSMB recommends unblinding. Treatment group-level unblinded analyses of subjects randomized in ordinal score category 6 may be conducted and published prior to the end of the trial to communicate the safety signal observed in this group by the DSMB during a safety review. If this analysis is conducted, only members of the unblinded analysis team will have access to subject-level treatment data while the study is ongoing; all other members of the study group will remain blinded to individual subject treatments as originally planned.

If AEs occur and investigators are concerned about the treatment allocation, the treatment can be discontinued. If a Serious Adverse Event occurs, that is thought to be related to the study drug, and the treating clinician believes that knowledge of the treatment arm may change the therapy provided to the patient, the individual subject can be unblinded. The procedure for unblinding will be further detailed in the Manual of Procedures (MOP).

4.2.7. Prior and Concomitant Therapy

See Section 6.5.1 of Appendix C of the study protocol for permitted concomitant therapy and procedures. See Section 6.5.2 of Appendix C of the study protocol for prohibited concomitant therapies.

4.2.8. Treatment Compliance

See Section 6.1.4 of Appendix C of the study protocol for details on dose modifications.

Each dose of study product will be administered by a member of the clinical research team who is qualified and licensed to administer the study product. Administration date and time will be entered into the case report form (CRF).

4.3. Efficacy and Safety Variables

For each study day while the patient is hospitalized, the clinical status will be recorded on an 8-point ordinal scale as follows:

- Day 1 – The clinical assessment at the time of randomization.
- Day 2 + - The most severe assessment occurring from midnight to midnight (00:00 to 23:59) of the prior day (e.g., the value recorded on Day 3 will be the most severe outcome that occurred on Day 2).

where the clinical status scale is defined as follows:

8. Death;
7. Hospitalized, on invasive mechanical ventilation or ECMO;
6. Hospitalized, on non-invasive ventilation or high flow oxygen devices;
5. Hospitalized, requiring supplemental oxygen;
4. Hospitalized, not requiring supplemental oxygen- requiring ongoing medical care (COVID-19 related or otherwise);
3. Hospitalized, not requiring supplemental oxygen - no longer requires ongoing medical care;
2. Not hospitalized, but new or increased limitation on activities and/or requiring new or increased home oxygen;
1. Not hospitalized, no limitations on activities

A modified version of the ordinal scale will be used in sensitivity analyses of the primary and secondary outcomes. The modified scale will be as follows:

8. Death;
7. Hospitalized, on invasive mechanical ventilation or ECMO;
6. Hospitalized, on non-invasive ventilation or high flow oxygen devices;
5. Hospitalized, requiring supplemental oxygen;
4. Hospitalized, not requiring supplemental oxygen- requiring ongoing medical care (COVID-19 related or otherwise);
3. Not hospitalized, but new or increased limitation on activities and/or requiring new or increased home oxygen;
2. Hospitalized, not requiring supplemental oxygen - no longer requires ongoing medical care; or Not hospitalized, no limitations on activities.

That is, category 1 and 3 of the original scale will be combined into the lowest category. This scale will be denoted as the “Modified Recovery” ordinal scale.

In review of study data and site data queries for ACTT-3 subjects who received study product after reaching ordinal score 6, the study team identified that there was ambiguity in the high-flow oxygen categorization. The language in the MOP allowed for different interpretation of high-flow oxygen use, where some clinical sites interpreted and entered any high-flow device use as Ordinal Score 6 while other sites used less than 15L on a high-flow device and entered this as Ordinal Score 5.

The original (as-classified by the site) ordinal scores will be used as the primary scoring method for analyses. The following modified ordinal scale will be used in sensitivity analysis of select outcomes:

8. Death;
7. Hospitalized, on invasive mechanical ventilation or ECMO;
6. Hospitalized, on non-invasive ventilation or high flow oxygen devices at oxygen flow rate greater than 15L/min;
5. Hospitalized, requiring supplemental oxygen or high flow oxygen devices at oxygen flow rate less than or equal to 15L/min;
4. Hospitalized, not requiring supplemental oxygen - requiring ongoing medical care (COVID-19 related or otherwise);
3. Hospitalized, not requiring supplemental oxygen - no longer requiring ongoing medical care;
2. Not hospitalized, but new or increased limitation on activities and/or requiring new or increased home oxygen;
1. Not hospitalized, no limitations on activities.

This scale will be denoted as the “Modified Oxygen Use” ordinal scale.

NEWS has demonstrated an ability to discriminate subjects at risk of poor outcomes. This score is based on 7 clinical parameters (see Section 8.1.2.3 in Appendix C of the study protocol). This should be evaluated at the first assessment of a given study day and prior to administration of study product. The 7 parameters can be obtained from the hospital chart using the last measurement prior to the time of assessment and a numeric score given for each parameter (e.g., a RR of 9 is one point, oxygen saturation of 92 is two points). This is recorded for the day obtained. i.e., on Day N, the Day N score is obtained and recorded as the Day N score.

Oxygenation, Non-invasive ventilation/high flow oxygen, Invasive Mechanical Ventilation / extracorporeal membrane oxygenation (ECMO), hospitalization and mortality will be assessed using results of the 8-point ordinal scale and post discharge eCRF questions.

Safety will be assessed by the following:

- Cumulative incidence of serious adverse events (SAEs) through 28 days of follow-up.
- Cumulative incidence of Grade 3 and 4 AEs.
- Discontinuation or temporary suspension of study product administration (for any reason).
- Changes in white cell count, hemoglobin, platelets, creatinine, total bilirubin, ALT, AST, and INR, d-dimer, C-reactive protein over time. Note D-dimer and CRP are not graded.

Clinical labs will be drawn on Days 1, 3, 5, 8, 11 and on Day 15 and 29 if the subject is able to return to the clinic or is still hospitalized. The Ochsner Medical Center Kenner site used both a standard and high-sensitivity assay for measuring CRP. As results from these assays are not

comparable, CRP values from the high-sensitivity assay will be excluded from all CRP summaries and any analyses that use CRP values.

Virologic efficacy is an exploratory endpoint and will be assessed by the following:

- Qualitative and quantitative PCR for SARS-CoV-2 in OP swab on Days 1, 3, 5, 8, 11 (while hospitalized); and Day 15 and 29 (if able to return to clinic or still hospitalized).
- Qualitative and quantitative PCR for SARS-CoV-2 in blood on Days 1, 3, 5, 8, 11 (while hospitalized).

The schedule of study procedures is provided in Section 1.2 of Appendix C of the study protocol.

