7.1.1.2 Subcutaneous Interferon beta-1a and Placebo Injections Halting

See [Section 6.1.4.](#) for information about dosing modifications due to laboratory abnormalities.

The subject should not receive any additional subcutaneous injections for the remainder of the study if a subject develops any of the following conditions during the study:

- Disease progresses to the point that the subject requires high-flow oxygen or other non-invasive ventilatory support (i.e., a category 6 on ordinal scale) or mechanical ventilation or ECMO (category 7). Note: even if they improve to a category 4 or 5 before study Day 7, no additional subcutaneous injections will be given.
- Anaphylaxis temporally associated with subcutaneous injection
- Seizures not attributable to COVID-19, a medical complication of COVID-19 or another medical condition
- Thrombotic microangiopathy including thrombotic thrombocytopenic purpura and hemolytic uremic syndrome thought to be due to interferon beta-1a
- ALT or AST >8 times ULN
- Suspected drug-induced liver injury with symptomatic disease (i.e., jaundice, right upper quadrant pain or tenderness, fatigue, nausea, vomiting, etc.)

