8.1.2.2 Ordinal Scale

The ordinal scale is the primary measure of clinical outcome. The scale used in this study is as follows (from worst to best), and categories 1, 2 and 3 represent recovery for a subject:

Category 8: Death;

Category 7: Hospitalized, on invasive mechanical ventilation or ECMO;

Category 6: Hospitalized, on non-invasive ventilation or high flow oxygen devices;

Category 5: Hospitalized, requiring supplemental oxygen;

Category 4: Hospitalized, not requiring supplemental oxygen – requiring ongoing medical care (COVID-19 related or otherwise);

Category 3: Hospitalized, not requiring supplemental oxygen – no longer requires ongoing medical care; This would include those kept in hospital for quarantine/infection control, awaiting bed in rehabilitation facility or homecare, etc.

Category 2: Not hospitalized, but new or increased limitation on activities and/or requiring new or increased home oxygen;

Category 1: Not hospitalized, no limitations on activities

To determine a subject's clinical status using the ordinal scale: On Day 1, report their clinical status at randomization. As there should be <24 hours between randomization and infusion, the ordinal scale at done at randomization suffices as the Day 1 ordinal scale. After Day 1, collect the ordinal scale daily while hospitalized from Day 2 through Day 29 by providing the worst clinical assessment for the previous day (i.e., midnight to midnight; 00:00 – 23:59 (24-hr clock)).

For those who are discharged prior to Day 15, collect ordinal scale on follow-up Days 15, 22 and 29 by providing the worst clinical assessment for the previous day (i.e., midnight to midnight; 00:00 – 23:59 (24-hr clock)). For example, on study Day 3 when completing the form, the worse clinical outcome measure of Day 2 is captured with the worst being death followed by ECMO, mechanical ventilation, etc. The Day 2 measurement is assessed as occurring anytime in that 24-hour period (00:00 to 23:59).

It is important to capture all deaths that occur during the study as this is one of the outcomes of the study. Death is a category on the ordinal scale. If a subject dies during the study, the site will need to complete an ordinal scale assessment for the day after death. If a subject dies within the window of the final study visit (i.e., Day 29 + 6-day window), complete an ordinal scale assessment on the day after death. For more information about the data collected for the ordinal scale, see the MOP.

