3.3.2. Recovery and Time to Recovery

The primary efficacy and one of the key secondary outcome measures is the time to recovery assessed through Day 29 + 6 days. Recovery will be defined as having a value of 1, 2, or 3 on the clinical status 8-point ordinal scale. The time to recovery will be defined as the elapsed time (in days) from randomization to the earliest day at which a subject reaches recovery. Note that since clinical status assessments are recorded as defined in Section 4.3, the day that is being assessed (not necessarily the day the response is collected) will be used to determine the timing of events. For example, a subject with a score of 5 recorded on Days 1-3 and a score of 3 recorded on

Day 4 will have a time to recovery equal to 3 days. It is also possible that a subject has a clinical status score > 3 reported for a particular day but was subsequently discharged on the same day. Such cases and other special cases will be reviewed by the Endpoint Review Committee or the NIAID Medical Officer, or her designee(s), to make the determination of whether the subject should be considered recovered in analyses. Subject data to be reviewed as part of this determination will include the reported clinical status scores while hospitalized, where the subject was discharged to (e.g. private residence, rehabilitation facility, long-term care/nursing home, comfort and care), and any information regarding readmittance. Subjects discharged to hospice or other end-of-life care will not be considered recovered. Additional information may be solicited to assess recovery.

Any subjects that are lost to follow-up or terminated early prior to an observed recovery will be censored at the day of their last observed assessment. Subjects who complete follow-up but do not experience recovery will be censored at the day of their Day 29 visit. All deaths that occur on or before Day 29 (and prior to any observed recovery) will be considered censored at 28 days. Note that we do not expect many subjects to worsen after discharge. However, we will evaluate whether any discharged subjects subsequently experience a worse clinical status and sensitivity analyses will be conducted accordingly. For these analyses, subjects who recover but are later readmitted for COVID-19 will not be considered a recovery but will instead be censored at 28 days.

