8.2.4. Incidence of New Oxygen use

The incidence and duration of new oxygen use will be analyzed by treatment arm. This will only include subjects in category 4 at randomization. New use will be identified by a post-randomization score of at least 5; the number of subjects reporting new use and the incidence rate (and CI) will be reported.

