8.2.6. Incidence of New Non-Invasive Ventilation/High-Flow Oxygen

The incidence and duration of new Non-Invasive Ventilation/High-Flow Oxygen use will be analyzed by treatment arm. This will only include subjects in category 4 or 5 at randomization. New use will be identified by a post-randomization score of 6. The number of subjects reporting new use and the incidence rate (and CI) will be reported.

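### The Day 2 ordinal form looks back over all of Day 1, so oxygen stopped before randomization can be counted as new use after it

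*SAP*

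**What the plan says.** **Baseline.** SAP 4.3 defines the Day 1 score as follows: "The clinical assessment at the time of randomization". Protocol Appendix C 8.1.2.2 agrees: "On Day 1, report their clinical status at randomization".

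**Later records.** From Day 2, SAP 4.3 records "The most severe assessment occurring from midnight to midnight (00:00 to 23:59) of the prior day". Appendix C 8.1.2.2 tells sites to "collect the ordinal scale daily while hospitalized from Day 2 through Day 29 by providing the worst clinical assessment for the previous day". Both documents illustrate this with the Day 3 form, which describes Day 2. Neither illustrates the Day 2 form.

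**New use.** SAP 8.2.4 looks only at subjects in category 4 at randomization: "New use will be identified by a post-randomization score of at least 5". SAP 8.2.6 looks at subjects in category 4 or 5: "New use will be identified by a post-randomization score of 6". SAP 9.4 adds time to death or progression to ventilation, invasive or of either kind, and states no start of window. SAP 4.3 says the oxygen and ventilation outcomes are taken from the ordinal scale and the post-discharge questions.

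**Timing.** For recovery, SAP 3.3.2 says "the day that is being assessed (not necessarily the day the response is collected) will be used to determine the timing of events". SAP 3.3.4 repeats this for improvement.

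**The concern.** Baseline is a status at one moment, but the first record after it describes a whole calendar day that began before that moment. If support was higher earlier on Day 1 and had been reduced by randomization, the Day 2 form shows a rise from baseline that did not occur after randomization. None of the sections above starts the first window at randomization, sets the Day 2 form aside, or requires that the support began after randomization.

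The incidence of new oxygen use and of new non-invasive ventilation or high-flow use are listed secondary objectives, and they ask what happens on treatment. Events that finished before assignment would be added to both arms. Reported incidence would be too high and the difference between arms too small. Durations are touched as well. The Table 33 shell summarizes days on oxygen for baseline-4 subjects only among those with new use, and SAP 3.3.8 counts every day scored 5, 6 or 7. A false new user can therefore enter that summary with one spurious day.

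**Working it through.** The plan gives no figure for same-day support before randomization, so there is nothing of its own to reproduce. The check has three parts.

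**1. How much of the window precedes randomization.** The Day 2 form covers 24 hours of Day 1. Randomization at 08:00 leaves 8/24 = 33% of them before assignment; 12:00 leaves 50%; 16:00 leaves 67%.

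**2. Worked records under the rule as written.**

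| Course on Day 1 | Score at randomization (14:00) | Day 2 form, 00:00–23:59 | Worst status after 14:00 |
|---|---|---|---|
| Oxygen until 09:00, then room air | 4 | 5 | 4 |
| High-flow 06:00–10:00, otherwise low-flow oxygen | 5 | 6 | 5 |

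The first patient meets the 8.2.4 trigger and the second meets the 8.2.6 trigger. Neither used more support after randomization than at it. Assigning the record to the day assessed does not help, because that day is still Day 1 from midnight.

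For recovery and improvement, the worst status on Day 1 cannot be better than the status at randomization, which is part of that day. Going through every combination of status before and after randomization, for baselines 4, 5 and 6, no Day 1 recovery or improvement call changed. The main Day 15 analysis uses the score at the Day 15 visit, whose window lies wholly after randomization.

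**3. Size.** Let p be the true new-use rate. Let f be the share of subjects without true new use who had a higher category earlier on Day 1, taken as equal in both arms.

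- Observed rate = p + (1 − p)f
- Observed difference = (p₁ − p₂)(1 − f)

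Neither f nor p is in the documents. The values below are assumptions.

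| True rates | f | Observed rates | Difference (points) |
|---|---|---|---|
| 30% v 22% | 0 | 30.0% v 22.0% | 8.0 |
| | 2% | 31.4% v 23.6% | 7.8 |
| | 5% | 33.5% v 25.9% | 7.6 |
| | 10% | 37.0% v 29.8% | 7.2 |
| | 15% | 40.5% v 33.7% | 6.8 |
| 15% v 10% | 0 | 15.0% v 10.0% | 5.0 |
| | 5% | 19.25% v 14.5% | 4.75 |
| | 10% | 23.5% v 19.0% | 4.5 |

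At 30% v 22% and f = 5%, the false events are 0.05 × 70 = 3.5 and 0.05 × 78 = 3.9 per 100 subjects at risk. The distortion is larger in the incidence itself than in the difference.

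**The case against.** **The term is open to another reading.** The SAP does not define a post-randomization score. A programmer could exclude the Day 2 form because it is timed to Day 1, or could hold that support ended before randomization is not post-randomization. Appendix C also refers to the MOP for more on ordinal data, and the MOP is not among these documents. This stands as a limit: the supplied text produces the miscount, but the miscount has not been shown in data. It does not remove the point. Excluding the form would also lose real escalation between randomization and midnight, and two readings would give two incidence rates.

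**The route through score 6 is narrow.** Exclusion 2 in Appendix C removes anyone in category 6 or 7 at screening. High-flow or non-invasive support on Day 1 must then fall outside the screening assessment and end before randomization. This stands for current enrolment; subjects enrolled before category 6 was closed on 4 September 2020 were not limited in this way. The step from 5 to 4, which drives 8.2.4, has no such barrier.

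**It favours neither arm and touches no main analysis.** That is right. No test is planned for new use.

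**A reader might infer a conflict with the injection-halting rule**, since Appendix C 7.1.1.2 says that "even if they improve to a category 4 or 5 before study Day 7, no additional subcutaneous injections will be given". The documents do not support this. The rule applies to conditions that develop during the study and is worded as disease progression to a level of support. Support that stopped before randomization is neither, so there is nothing there to reconcile.

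**Conclusion.** As written, the rule records support that ended before randomization as a post-baseline rise. The plausible effect is on new oxygen use in baseline-4 subjects (SAP 8.2.4). It is smaller for new non-invasive ventilation or high-flow use (SAP 8.2.6) and for the SAP 9.4 endpoint that includes non-invasive ventilation. Days of support can gain at most one day. Only support used on the calendar day of randomization is caught.

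The effect is non-differential, because it arises before assignment. Incidence rises in both arms and the planned rate difference shrinks by (1 − f). The hazard ratio in SAP 9.4 would be pulled toward 1, by an amount the documents do not allow one to compute. All sizes rest on assumed values of f and of the true rates, and on f being equal between arms.

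Two stronger readings are not supported. A reader might extend the point to new invasive ventilation (SAP 8.2.8). Category 7 was not enrolled at any stage, and nothing suggests patients moving from 7 to 4, 5 or 6 earlier on the day of randomization. A reader might also express the loss as a ratio of rates, which looks larger, but the contrast planned in the Table 33 shell is a difference in rates.

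**What to change.** In Appendix C 8.1.2.2 and SAP 4.3, define the Day 2 form as the worst status from the time of randomization to 23:59 of Day 1. This costs one sentence in each document.

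For data already collected, state in SAP 8.2.4, 8.2.6 and 9.4 which record is the first eligible post-randomization score. Add a sensitivity analysis that counts new use or progression only from the record describing Day 2 onward, that is, from the Day 3 form. Its cost is the loss of true events confined to the hours between randomization and midnight of Day 1. Those hours may include the first injection, in a trial where category 6 raised a safety concern, so this should not replace the main analysis. If the main analysis keeps the Day 2 form, the two counts bracket the true incidence in each arm: the main one can only overcount through this route, and the sensitivity one can only undercount.
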